## **Abstract**

Tracheal intubation of infants and children is a critical lifesaving skill, and its importance is recognized by the Accreditation Council on Graduate Medical Education (ACGME), Residency Review Committee (RRC), the Neonatal Resuscitation Program (NRP) and Pediatric Advanced Life Support (PALS) programs. Despite its importance, current training is lacking in teaching this critical procedural skill as demonstrated by the inability of up to 1/3 of upper level Pediatric residents to be able to successfully intubate Very Low Birth Weight (VLBW, <1500 grams) neonates. New technology, which has now been adapted to the existing telemedicine network in Arkansas, offers an exciting opportunity to improve the ability of pediatric trainees to accomplish this critical task. We will utilize a deliberate practice approach with immediate feedback during neonatology rotations using the Storz video laryngoscope to teach this critical skill to Pediatric and Med-Peds residents (n=95 residents total). Previous work demonstrated improvement in skills with a manikin, but it is unknown if these skills will translate to live intubations. The residents will receive training during alternating months, and will be recorded during live intubations. We will assess how intubation skills using a manikin translates to live patients. We anticipate this training will dramatically improve intubation skills and resident confidence as evidenced by intubation accuracy.

## **Project Narrative**

### **Background and Significance**

Tracheal intubation is one of the most important interventions in the stabilization of critically ill or injured children. Advanced airway skills training is one of the major pillars of the ACGME pediatric program requirements for resident and fellowship education (Accreditation Council for Graduate Medical Education, 2007). The pediatric airway presents unique anatomic challenges depending on the patient age, size and underlying condition. These challenges, coupled with low frequency of pediatric trainee exposure to advanced airway management, make tracheal intubation procedural competency difficult to achieve. As a result, tracheal intubation in infants and children is associated with high levels of operator stress as well as patient morbidity and mortality.

The ability to manage the pediatric airway, which includes anticipating potential difficulties and choosing an appropriate approach, remains one of the most vital skills to develop when caring for critically ill children. Provider training level has been found to correlate with patient outcome during advanced airway management in selected environments including the operating room, delivery room and Neonatal Intensive Care Unit (NICU). Pediatric trauma patients intubated by less experienced emergency medical personnel in the field have increased morbidity and mortality when compared to similar patients intubated by pediatric-trained hospital personnel. A limited number of studies from neonatal resuscitation demonstrated that resident trainee success rates are moderate at best, with 1/3 of upper level pediatric residents unable to intubate a very low birth weight (<1500 grams) neonate. The RRC agreed that neonatal intubation is a critical skill, but respondents to a survey sent to Residency Program Directors determined that "many residents do not develop competence in that area" and that a "more robust and standardized method is needed for teaching procedural skills and for documenting

Version #3

Date: September 19, 2017

pg. 2

competence". A survey of pediatric emergency room directors found that the number of intubations necessary to maintain skill in this area was inadequate. Even more concerning is that procedural skills such as intubation deteriorate rapidly over time (within the first year).

Our findings suggest that the training of pediatric residents is not sufficient prior to "live" tracheal intubations in the critical care setting. The current one to two days of airway management training as a part of resuscitation training (such as PALS or NRP) is not sufficient to provide safe intubation skills. A new approach to the instruction of tracheal intubation is needed for pediatric trainees, to decrease adverse events and to improve patient safety. One approach would be to develop and implement tracheal intubation training using concepts of deliberate practice modeled after Ericsson. The concepts include focused training on a specific task, immediate feedback, time for problem solving and evaluation, and opportunities for repeated performance. All pediatric residents will be required to meet a pre-set training goal (intubating a manikin consistently within 15 seconds, half the time allowed by NRP) in a simulation setting with intense, repeated training with feedback. This proposal is an attempt to develop such a training model.

Video laryngoscopy offers a potential solution to the problem of intubation training, because it allows the educator to actually "see" what the trainee is seeing with the laryngoscope. Although this mode of intubation has been used for some time with adult laryngoscopy, the technology has only recently been adapted for neonatal and pediatric use. One recent study found satisfaction with the proposed equipment, but patients were not randomized and its use in training has not been studied. The GlideScope, another brand of video laryngoscopy, has been used in children, providing better views, but intubation takes longer using this technology, and it does not adapt well for use in neonates and infants because of blade size. Interestingly, Skype has been used with this technology, but Skype offers limited resolution and is not HIPAA compliant. *We have been able to demonstrate that this equipment significantly decreases intubation times in manikins. Now we must determine if this improvement translates into improved intubation skill in live patients.*

### **Hypothesis and/or Specific Aims or Objectives**

Specific Aim 1. *Assess the impact of this educational manikin intervention on live patients.*

We hypothesize learners in the Intervention Group vs. the Control Group will have enhanced success in intubation as determined by the number of attempts and time required for intubation of live patients.

Specific Aim 2. *Assess the satisfaction of this educational intervention and equipment.*

We hypothesize pediatric residents will have increased satisfaction scores and confidence for intubating live patients in the Intervention Group vs. the Control Group.

Specific Aim 3. *Assess the association of confidence in intubation with actual success in intubation.*

We hypothesize increased confidence will be associated with increased intubation success.

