During the monthly rotation of each resident, ongoing data will be collected on the residents' ability to successfully intubate on the first attempt, the total number of attempts to intubate, and the total number of successful attempts at intubating a neonate within 30 seconds, the time limit set by NRP. All live intubations performed in the Stabilization Rooms will be recorded and reviewed by designated members of the NICU Safety Committee. The recorded videos of study participants will also be reviewed by [name] and [name], R.N. The information obtained from the video recordings will be kept in a safe, secure file that is password protected. At the end of the monthly rotation each resident, including those in the Control Group, will be offered the opportunity to complete the Hands-on Intubation training simulation with [name].

Angel Eye Cameras and control modules will be placed on the patient beds in the NICU Resuscitation Rooms which will be used for recording and monitoring infant intubation procedures. The cameras will be placed on the bed above the infant and staff while the control panel will be on a nearby wall to allow for easy starting and stopping of recording and monitoring of recording during the procedure. The control panel will have access to start/stop

[figure not shown]

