Study Title: *“Manikin To Patient Intubation: Does It Translate?”*

Principal Investigator: R. [name].
University of Arkansas for Medical Sciences
[name]
[name]
[contact]
Email: [contact]

Study Location: University of Arkansas for Medical Sciences
[name]
[name]

Date: September 19, 2017

NCT number: NCT03046966

Statistical Analysis

Chi-square tests with the Benjamani-Holm p-value correction to account for test multiplicity will be used to analyze the difference in baseline measures and demographics. Chi-square testing will be utilized for comparing end of survey comfort. Logistic regression will be utilized to compare overall and first-time intubation success rates between the control and intervention groups. Logistic regression will be used to compare the difference in success rate between training level groups. To account for over-dispersion, a negative binomial regression will be utilized to assess difference in overall and first-time intubation success counts.

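### Aim 1 names time to intubate, but the SAP has no analysis of time, leaves success undefined, and tests attempts only in reduced form

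*Protocol*

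**What the plan says.** **Protocol, Hypothesis and/or Specific Aims or Objectives (Specific Aim 1).** The Intervention Group is expected to do better than the Control Group, judged by "the number of attempts and time required for intubation of live patients".

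**Protocol, Background and Significance.** Earlier work is said to have shown that "this equipment significantly decreases intubation times in manikins". The trial is to find out whether this carries over to skill in live patients. The manikin training goal is itself a time, 15 seconds.

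**Protocol, Methods.** Three items are collected during the rotation. One is whether the resident succeeds at the first try, another is a count of all tries, and the last is a "total number of successful attempts at intubating a neonate within 30 seconds, the time limit set by NRP". Time in seconds is not on this list. Live intubations in the Stabilization Rooms are video recorded and reviewed. Allocation is by the month of the NICU rotation.

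**SAP, Statistical Analysis.** "Logistic regression will be utilized to compare overall and first-time intubation success rates between the control and intervention groups". Logistic regression also compares success between training levels, and negative binomial regression compares overall and first-time success counts. No model has time or number of attempts as its outcome, and success is not defined.

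**The concern.** Aim 1 names two yardsticks, attempts and time. The SAP's single paragraph lists every planned analysis, and time is in none of them. If success there means a tube placed at any time, the results say nothing about speed. If it means a tube placed within 30 seconds, speed enters only as yes or no. Because the SAP does not say which, the choice could be made after the videos have been reviewed.

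The trial's own prior evidence was on time. A training effect that appears mainly as faster intubation is therefore the effect the investigators have most reason to expect, and the plan has no stated test for it.

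**Working it through.** **1. Aim 1 measures traced through the documents**

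| Measure | Aim 1 | Collected (Protocol, Methods) | Analysed (SAP) |
|---|---|---|---|
| Number of attempts | Yes | Yes, as a total | Only as first-time success (one attempt versus more) and possibly as the denominator of the overall rate |
| Time in seconds | Yes | Not listed | No |
| Success within 30 seconds | Not named | Yes, as a count | Unclear, because success is undefined |

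The time part of Aim 1 thus has no stated test. The attempts part has one in reduced form.

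**2. The plan's own figure.** The Evaluation Plan gives 27 residents per group, but no outcome, effect, SD, alpha or power, so it cannot be reproduced. Solving backwards with d = (z_alpha + z_power) × sqrt(2/27), at two-sided 0.05 and 80% power:

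d = (1.960 + 0.842) × 0.272 = 0.76.

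Other choices give 0.88 (two-sided, 90%), 0.68 (one-sided, 80%) and 0.80 (one-sided, 90%). The documents do not say which applies, or to which outcome.

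**3. Illustration with repeated attempts.** All inputs except the group sizes are assumptions: 4 attempts per resident, times 25% shorter in the Intervention Group, log-SD 0.35 between and 0.5 within residents, and control medians of 25, 35 and 45 seconds. The 40 per group assumes that the 80 residents expected in Methods split evenly.

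- Variance of a resident's mean log time: 0.35² + 0.5²/4 = 0.1225 + 0.0625 = 0.185, so SD = 0.430.
- Shift: ln(0.75) = -0.288, so d = 0.288/0.430 = 0.67.
- Normal approximation at 27 per group: 0.67 × sqrt(27/2) = 2.46, and power = Φ(2.46 - 1.96) = Φ(0.50), about 69%.

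Simulation with 4,000 replicates per setting, using t-tests on resident means and on resident proportions, gave:

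| Per group | Log time | Share within 30 s |
|---|---|---|
| 27 | 66-68% | 52-56% |
| 40 | about 84% | 70-74% |

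**4. Sensitivity at 27 per group.** With log-SDs of 0.5 between and 0.7 within residents, a 35-second median and 4 attempts, power is about 41% against 34%. With one attempt each at the SDs in step 3, it is about 40% against 24%.

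**5. A second model.** Take one normal value per resident and d = 0.76, so that continuous time has 80% power at 27 per group. Cutting the same outcome at a time limit gives p2 = Φ(z(p1) + d). For p1 = 0.50, p2 = 0.78 and power is 57%. Over control success of 20-80%, power is 36-59%, and 44-81 per group are needed for 80%.

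**6. Limits of these figures.** They compare continuous time with a 30-second cut. They do not measure the loss from any-time success. Every simulated attempt ends in success, and clustering by month is ignored.

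**The case against.** The strongest defence is that the only total count of successes in the Protocol is "the total number of successful attempts at intubating a neonate within 30 seconds". The SAP's overall success counts can be read as that variable, in which case time does enter. The Background asks whether the manikin gain becomes better intubation skill, and the Abstract expects the evidence to be accuracy. Success outcomes fit both. Seconds were never on the collection list, so the SAP did not drop them.

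Much of this stands, and it rules out three stronger readings that a reader might infer:

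- *That the SAP analyses neither Aim 1 measure.* First-time success is the number of attempts reduced to one versus more than one, so the attempts part has a test.
- *That a slow success counts the same as a fast one.* This would follow only if success had no time limit. The SAP is silent, so the documents support only that success is undefined.
- *That the SAP discarded a more informative outcome.* The documents give no distribution for time, and the Protocol lists only the 30-second count.

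The defence does not remove the gap. Even on the favourable reading, the SAP never states the 30-second limit, while Aim 1 promises the time required and not only a threshold.

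**Conclusion.** The point holds in this limited form. Time is a named Aim 1 measure with no stated analysis, success is undefined, and attempts are analysed only in reduced form. This part rests on the text alone. It should be corrected before analysis.

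The size is uncertain. Analysing continuous time instead of a 30-second cut gains about 10 to 16 percentage points of power at 27 per group under the step 3 assumptions (66-68% against 52-56%). The gain is 7 points (41% against 34%) with larger SDs and 16 points (40% against 24%) with one attempt each. The one-value-per-resident model gives 21 to 44 points (80% against 36-59%). The direction is the same throughout, but the SDs, the effect and the attempts per resident are assumed. Allocation by month would reduce the absolute powers.

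**What to change.** 1. **Define success.** State in the SAP that success means intubation within 30 seconds, matching the Protocol's Methods section, with any-time success as a sensitivity analysis.
2. **Collect and analyse time.** Add time in seconds per attempt to the planned video review, with the start and end points written down. Add an Aim 1 time-to-success analysis by arm, adjusted for training level, that allows for repeated intubations per resident and for allocation by month. Failed attempts stay in as never successful, carried to a common maximum time. They are not dropped and not censored at abandonment. A mixed model on log time is not an equal alternative, because a failed attempt has no time to success and could not be included.
3. **Analyse attempts.** Make the number of attempts per intubation the second Aim 1 measure, with the same allowance for resident and month.
4. **Fallback.** If seconds cannot be read from the video, reword Aim 1 to claim only success within 30 seconds and first-attempt success.

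The cost is one timing field on a review already planned and a few sentences in the SAP. No extra residents, patients or procedures are needed.

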### **Target Audience**

Version #3

Date: September 19, 2017

pg. 3

The target audience will be Pediatric and Med-Peds residents. Total n = 95 potential participants

## **Methods**

This research study will include 95 resident physicians. We anticipate 80 residents will enroll, similar to our previous study in which 82 residents participated. Residents will be randomized to the Intervention Group or the Control Group. This study will be explained to potential participants as they begin their assigned rotation to the Neonatal Intensive Care Unit (NICU). The explanation of the study and the Information Sheet will be introduced during the first five (5) days of this rotation. Residents will be allowed to ask any questions they feel necessary and take as much time as needed in order to make a fully informed voluntary consent. It will be explained that their participation in this study is completely voluntary and a decision to not participate will have no impact on their training or standing in the residency program. Randomization will occur by the month the resident is assigned to the NICU.

All participants will:

- Receive NRP training and certification offered at the beginning of their residency
- Complete a Baseline Survey
- Complete a Baseline Cognitive and Simulation Assessment
- Have a Stabilization Room video recording as part of the quality improvement process for neonatal resuscitation
- Complete a Cognitive and Simulation Assessment at the end of the month
- Complete an End of Rotation Survey

Residents who are randomized to the Intervention Group will, in addition:

- Observe a 7 minute NRP video
- Complete a hands-on intubation simulation with [name] instructing:
  - Using state of the art technology, a Storz C-MAC video laryngoscope
  - Identifying anatomical landmarks
  - Practice on the manikin until intubation occurs within 15 seconds

During the monthly rotation of each resident, ongoing data will be collected on the residents' ability to successfully intubate on the first attempt, the total number of attempts to intubate, and the total number of successful attempts at intubating a neonate within 30 seconds, the time limit set by NRP. All live intubations performed in the Stabilization Rooms will be recorded and reviewed by designated members of the NICU Safety Committee. The recorded videos of study participants will also be reviewed by [name] and [name], R.N. The information obtained from the video recordings will be kept in a safe, secure file that is password protected. At the end of the monthly rotation each resident, including those in the Control Group, will be offered the opportunity to complete the Hands-on Intubation training simulation with [name].

Angel Eye Cameras and control modules will be placed on the patient beds in the NICU Resuscitation Rooms which will be used for recording and monitoring infant intubation procedures. The cameras will be placed on the bed above the infant and staff while the control panel will be on a nearby wall to allow for easy starting and stopping of recording and monitoring of recording during the procedure. The control panel will have access to start/stop

[figure not shown]

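### Arm is set by calendar month, the month pattern is described in two ways, and the success models carry no time term: a small repeating offset under alternation, a larger error-rate problem under unrestricted random months

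*Protocol*

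**What the plan says.** The protocol describes allocation in two places.

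- Methods: "Residents will be randomized to the Intervention Group or the Control Group", and later in the same paragraph "Randomization will occur by the month the resident is assigned to the NICU".
- Abstract: "The residents will receive training during alternating months".

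Neither place gives a sequence, a starting arm, an allocation ratio or any blocking.

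On analysis, the SAP states "Logistic regression will be utilized to compare overall and first-time intubation success rates between the control and intervention groups" and adds that "a negative binomial regression will be utilized to assess difference in overall and first-time intubation success counts". It names no calendar-time term in either model. Training level is compared in a separate sentence and is not given as a covariate in the arm comparison. Baseline measures are tested for difference but not adjusted for.

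On skill over time, every participant will "Receive NRP training and certification offered at the beginning of their residency". The Background section reports that procedural skill, intubation included, is lost quickly, within the first year.

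**The concern.** All residents in a given month share an arm, so arm is a function of calendar month. If a resident's skill also depends on the month, part of any skill trend enters the comparison of arms. The protocol gives some reason to expect a trend: formal training comes at the start of residency and skill is said to fade within a year. Experience with live patients could push the other way. Training level would not capture such a change even as a covariate, because the change occurs within a training year.

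How much this matters depends on the month pattern. Alternation interleaves the arms but fixes which one comes second. Freely randomised months have no fixed direction but can leave one arm well ahead of the other in a given trial. The plan leaves both readings open, and its success models protect against neither.

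**Working it through.** **Inputs from the documents.** Allocation by month (protocol, Methods); alternating months (protocol, Abstract); 80 residents expected, about 40 per arm (Methods); 27 per group planned (Evaluation Plan); no time term (SAP).

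**Assumptions, not in the documents.** A 12-month run; residents spread evenly over months; a linear change in success of 10, 20 or 30 points from the first to the last month (11 steps); success near 50% at mid-year; no true training effect. The calculations concern success rates. The negative binomial count models were not simulated.

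**The plan's own figure.** The 27 per group cannot be reproduced, because no error rate, power or effect size is given. As a yardstick only: at two-sided 5% and 80% power (assumed), 27 per group would detect, for example, 50% versus 85%, a difference of 35 points.

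**Step 1. Lag between arms in mean calendar month.**

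- Strict alternation: months 2, 4, …, 12 average 7 and months 1, 3, …, 11 average 6, so the lag is 1.0 month. Because 12 is even, each calendar month falls in the same arm every year. Over 24 months the lag is still 1.0.
- Unrestricted random 6:6 split: the sample variance of 1 to 12 is 13, so the lag has SD √(13 × (1/6 + 1/6)) = √4.33 = 2.08 months. Enumerating all 924 splits gives the same SD, a 39% chance of a lag of 2 months or more, and a maximum of 6 months.
- Random order within consecutive two-month pairs: each of six pairs adds +1/6 or −1/6 month, so the mean is 0, the SD is √6/6 = 0.41 and the maximum is 1.0.

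**Step 2. Shift in the success difference** = (change over the year ÷ 11) × lag.

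| Assumed change | Alternation (fixed) | Random 6:6 (SD) | Random within pairs (SD) |
|---|---|---|---|
| 10 points | 0.9 | 1.9 | 0.4 |
| 20 points | 1.8 | 3.8 | 0.7 |
| 30 points | 2.7 | 5.7 | 1.1 |

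**Step 3. Rejection by a nominal 5% test with no training effect.**

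- Alternation: a two-proportion normal approximation gives 5.1 to 5.5% at 27 per arm and 5.1 to 5.7% at 40 per arm, over changes of 10 to 30 points. Simulation with 80 residents and 20 to 30 points gives about 5 to 7%.
- Unrestricted random months, no time or month term: the approximation averages 6.3% (20 points) and 8.0% (30 points) at 40 per arm. Simulation gives about 7 to 8% with one intubation per resident and 9 to 13% with three. Repeated intubations make it worse because the naive standard error shrinks while the shift does not.
- Unrestricted random months, with allowance made: adding a linear time term gives about 4 to 5%. A t-test on month means with no time term gives 4.7 to 5.2%.
- Random order within pairs: about 4 to 6% in the settings run, even without a time term.

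**The case against.** The strongest reply is that the Abstract gives the only month pattern in the documents, and that pattern already balances most of calendar time. This stands. A reader might infer that the allocation does nothing about calendar time; the documents do not support that, because alternation limits the lag to one month. A bias of at most 2.7 points is small beside a yardstick of 35.

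The second reply is that the larger rejection rates need unrestricted random months, which no passage spells out, and that under such months the estimate is unbiased on average. This also stands: the excess rejection is a standard-error problem, and an analysis that accounts for month corrects it. A reader might take those rates as evidence of a systematic bias, and they are not. What remains is that Methods speaks of randomisation by month without restriction, so this reading is open, and the SAP has no month term either. Nor would a month-level analysis remove the fixed offset under alternation.

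Third, the premise of a trend is thin. The Background statement supports loss of skill, at most for first-year residents, and gives no size. The participants are Pediatric and Med-Peds residents generally. The 10 to 30 points, and even the sign, are assumptions.

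A reader might also infer that an arm could fall below the planned 27. That requires arms chosen by coin toss each month, and much of the risk comes from a 4:8 split of 12 months, which gives 80 × 4/12 = 26.7 residents against 27. Alternation gives about 40 per arm. The point should not be made.

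**Conclusion.** The concern holds in a limited form. Arm follows calendar month, the Abstract and Methods describe the month pattern differently, and no success model includes time.

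Under alternation the result is a small offset that repeats every year: 0.9 to 2.7 points for an assumed change of 10 to 30 points, of unknown sign, with rejection of about 5 to 7% for 20 to 30 points. Under unrestricted random months there is no average bias, but ignoring both time and month raises rejection to about 7 to 8% with one intubation per resident and 9 to 13% with three, for the same assumed 20 to 30 points.

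The two statements could be made compatible, for example by a random starting arm followed by alternation, but the plan does not say so, and the one-month lag would then still be fixed throughout the trial. The issue is of minor to moderate size and worth correcting because the correction is cheap.

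**What to change.** - **Reconcile the Abstract and Methods** by stating one month sequence. Randomise the order of the two arms within each consecutive two-month pair. This keeps the balance of alternation, removes the fixed direction and brings the SD of the lag to 0.4 months.
- **Add time in the training year** as a prespecified term in the logistic and negative binomial models for overall and first-time success. A linear term is enough for a steady trend. Pair terms are an alternative, but only if the order within pairs is randomised; under alternation the same arm would always be second in the pair and the offset would remain.
- **Do not treat the time term as a substitute** for allowing for residents who share a month or for repeated intubations by one resident. Those affect the standard error and need their own provision.

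The cost is a new month list and one SAP term: one degree of freedom if linear, more with pair terms. The second month of each pair is predictable once the first is known, so the list should be held outside the unit.
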